Official Title: AMPLIFY: Amplifying Sensation in Underactive Bladder

Protocol#: Pro00106457 Version 1.17

NCT#: NCT04516434

Document Date: 04/10/2024

Standard Research Summary

Purpose of the Study

Objectives & hypotheses to be tested

The overall objective of this study is to improve lower urinary tract symptoms (LUTS) in adult neurologically-intact women with underactive bladder through electrical stimulation of bladder sensory nerves or urethral sensory nerves. The first primary endpoints are that sensory nerve fiber stimulation to the bladder will decrease bothersome urinary symptoms during filling and emptying, stimulation to the urethra will decrease bothersome urinary symptoms during emptying, and that bladder stimulation will increase bladder sensation during filling and emptying, as determined by our lower urinary tract symptom questionnaire. The second primary endpoint is that sensory nerve fiber stimulation to the bladder or urethra will increase bladder emptying during pressure-flow studies in participants with poor baseline bladder function. In addition to these primary endpoints, we will also observe secondary endpoints that will be compared to paired baseline measurements. Secondary endpoints include (a) increased bladder or urethral current perception threshold relative to normative data, (b) decreased bladder volumes at cystometric endpoints with intravesical (bladder) electrical stimulation, and (c) increased detrusor contraction strength and contraction duration with intraurethral electrical stimulation.

Background & Significance

• Should support the scientific aims of the research

The storage and elimination of urine is regulated by neural circuits in the brain and spinal cord to coordinate function between the urinary bladder and the urethra (Fowler et al. 2008). During micturition (bladder emptying), the elimination of urine is facilitated by bladder muscle (detrusor) contraction and urethral and pelvic floor muscle relaxation. Urine flow through the urethra also activates sensory nerves to amplify bladder contractions and maintain efficient bladder emptying (Jung et al. 1999, Bump 2000). Incomplete emptying and urinary retention occur when these mechanisms are disrupted or poorly coordinated.

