bladder or urethra is investigational and not standard clinical practice. However, intravesical (bladder) electrical stimulation has been used in persons with detrusor underactivity (Gladh et al. 2003, Deng et al. 2017), overactive bladder (Yune et al. 2018), and neurogenic non-obstructive urinary retention (Lombardi et al. 2013). Intraurethral electrical stimulation has also been used in persons with spinal cord injury (Yoo et al. 2011), as well as in women with urgency urinary incontinence (Pro00084173). Achieving the proposed objectives will establish a prognostic marker for rationally guided electrical stimulation in women with underactive bladder. Understanding how these mechanisms contribute to impaired emptying in underactive bladder will enable the development of novel therapeutics to enhance quality of life.

There are no patents, conflicts of interest, or FDA submissions in the works related to this study.

Design & Procedures

Describe the study, providing details regarding the study intervention (drug, device, physical procedures, manipulation of the subject or the subject's environment, etc.). Discuss justifications for placebo control, discontinuation or delay of standard therapies, and washout periods if applicable. Identify procedures, tests and interventions performed exclusively for research purposes or more frequently than standard of care. Include alternative therapies, concurrent therapies discontinued per protocol, risk benefit ratio, and use of tissue/specimens. Discuss monitoring during washout periods if applicable. Include brief description of follow-up, if any.

We will only be evaluating adult women in this proposal. Men are excluded from this pilot study due to the high incidence of similar symptoms caused to a degree by prostatic hyperplasia and not necessarily an underactive bladder. Patients will be screened through Chart Review and on the phone to determine eligibility, and if found eligible, will be scheduled for an in-person study procedure visit at the Duke Urogynecology Office at Patterson Place, Durham, NC under the supervision of [name], MD.

Design

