Study procedure visit: Participants will be reminded by phone call or email 48 hours before the study visit to withdraw from medications affecting urination per our inclusion criteria. On the day of the visit, participants will sign and date the informed consent document and complete a compensation form, LURN SI-29 questionnaire survey, and demographics questionnaire survey. Pre-procedure vital signs, point of care urinalysis, and a pregnancy test will be obtained. Participants will be excluded with a positive pregnancy test or delayed until resolution of infection with a positive urinalysis (per exclusion criteria). If participants have negative urinalysis, negative pregnancy test, and meet inclusion/exclusion criteria they will undergo current perception threshold (CPT) testing in the bladder and urethra.

Participants will be assigned to the intervention arm based on CPT. CPT data will be analyzed immediately by percentage change against normative data to stratify investigational allocation to intravesical (bladder) electrical stimulation or intraurethral electrical stimulation (Kenton et al. 2007). The allocation will be as follows: 1) if percentage change of urethral CPT > percentage change of bladder CPT then participants will receive intraurethral electrical stimulation, 2) if percentage change of bladder CPT > percentage change of

urethral CPT then participants will receive intravesical electrical stimulation, or 3) if percentage change of urethral CPT = percentage change of bladder CPT then participants will receive intravesical stimulation when cystometry "first desire to void" > 275ml or intraurethral stimulation when pressure-flow detrusor pressure at maximum flow < 30 cmH2O and maximum flow < 10 ml/s. After the investigational session of stimulation, participants will undergo post-study urodynamic studies which will include cystometry and pressure-flow studies. At the completion of these procedures, participants will be given standard urogynecology post urodynamic study instructions. They will also be instructed to complete remotely a post-study condition LURN SI-29 questionnaire that will be emailed via RedCap 7 days after the study visit. At that time, they will be considered to have completed the study.

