Uroflowmetry This standard procedure may be performed if participants are unable to void past the catheters in pressure flow studies. The dual chamber bladder catheter will be removed, and the participant will be instructed to void while sitting on a commode chair. A postvoid residual volume will be measured by straight catheterization. Variables that will be recorded include the following: voided volume, postvoid residual volume, flow rate, flow quality, and voided percentage. While this test sacrifices our secondary study objectives, we will still be able to fulfill our primary objectives of improved sensation and improved voiding function if the participant can void without catheters.

Selection of Subjects

• List inclusion/exclusion criteria and how subjects will be identified.

Inclusion Criteria:

- Females ages 18 and older
- Able to provide informed consent and agree to the study risks
- Willing to withdraw from medications affecting urination for the 48 hours prior to the procedure (e.g., alpha-adrenergic antagonists, cholinergic agonists, cholinesterase inhibitors)
- Has the below response to 2 of the 3 bulleted questions:
 - Questions regarding self-reported poor sensation during bladder filling or emptying (one or more of the below)

Question: In the past 7 days, where did you feel sensations when you felt you needed to urinate? Answer: "No" response for Bladder Area

Question: In the past 7 days, how often did you have no sensation of urine flow while you were urinating?

Answer: "Most of the time" or "Every time" response

Question: In the past 7 days, how often did you feel that your bladder was not completely empty after urination?

Answer: "Most of the time" or "Every time" response

Questions regarding self-reported bothersome urinary symptoms (one or more of the below)

Question: In the past 7 days, how satisfied were you with your bladder function? Answer: "Not at all satisfied" or "Somewhat satisfied" response

Question: In the past 7 days, how bothered were you by urinary symptoms?

Answer: "Very bothered" or "Extremely bothered" response

 Standard uroflowmetry with a voiding efficiency (voided volume / voided volume + residual volume) of < 80%, voided volume + residual volume must be >150ml for measurement

Exclusion Criteria:

- Preexisting neurological impairment (e.g., spinal cord injury, multiple sclerosis, Guillain-Barre, cauda equina syndrome, cerebrovascular accident, Parkinson's disease, traumatic brain injury)

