- There is a risk of painful sensations from electrical stimulation to the bladder and urethra. Participants can elect to decrease or terminate stimulation at any point during the study. We will minimize the risk of activating nerve fibers carrying painful stimuli by individually adjusting current amplitude to 80% of their maximum tolerable intensity. Every subject will be titrated down from a stimulation parameter that they feel is uncomfortable. The stimulation amplitude will be guided by the values obtained from the Current Perception Threshold forced choice paradigm, where a baseline intensity alignment automatically increases amplitude until the participant reports detection. Participants will be informed of any sensations they may perceive as unpleasant and may elect to terminate stimulation at any point.
- Participating in this study while pregnant may expose the unborn child to unknown risks. There is no risk level because we have excluded pregnant women.

- There may be some unknown and unforeseeable risks related to the study. Participants will be informed of any significant new information learned during the study that might cause them to change their mind about participating in the study. Significant new findings developed during the research, which may relate to their willingness to participate will also be provided to them.

Costs to the Subject

• Describe and justify any costs that the subject will incur as a result of participation; ordinarily, subjects should not be expected to pay for research without receiving direct benefit.

There will be no cost to the subject as a result of the participation.

Data Analysis & Statistical Considerations

Describe endpoints and power calculations. Provide a detailed description of how study data will be
analyzed, including statistical methods used, and how ineligible subjects will be handled and which
subjects will be included for analysis. Include planned sample size justification. Provide estimated time
to target accrual and accrual rate. Describe interim analysis including plans to stop accrual during
monitoring. Phase I studies, include dose escalation schema and criteria for dose escalation with
definition of MTD and DLT.

Expected enrollment n = 20 neurologically-intact women with underactive bladder **Expected effect size** (dz) = 0.67 **Power (1 – \beta) =** 0.8

Time to Target Accrual 2 years

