To account for participants failing to meet our eligibility criteria, it is anticipated that a total of 100 adult women will be screened to achieve n=20 total study participants. We expect to screen all patients with ICD codes suggestive of underactive bladder because a DEDUCE query revealed that in 2019 Duke Urogynecology clinics saw 34 patients meeting our criteria and approximately 10 of those patients went on for urodynamic studies. It is our expectation that the lack of consistent terminology and diagnostic parameters for underactive bladder will result in a large patient population failing to meet our eligibility criteria. Our expected enrollment will enable detection of a 7.5% change in voided percentage after stimulation with power (1-beta) of 0.8.

Statistical Methods

Primary Aim 1: Use of intraurethral electrical stimulation or intravesical electrical stimulation to assess increase in voided percentage during pressure-flow studies

Hypothesis: Electrical stimulation will increase voided percentage, and this hypothesis will be evaluated with non-parametric tests.

Method: Data will be analyzed by Wilcoxon signed-rank test to determine the influence of intravesical and intraurethral stimulation on bladder emptying.

Primary Aim 2: Use of LURN SI-29 questionnaire to assess whether electrical stimulation decreases urinary bothersome symptoms and increase bladder sensation during filling and emptying

Hypothesis: Intravesical (bladder) stimulation will decrease affirmatory responses to bothersome urinary symptoms and increase affirmatory responses to sensation during filling and emptying, whereas intraurethral stimulation will decrease affirmatory responses to bothersome symptoms during emptying.

Method: Data will be analyzed by the McNemar Exact Test or the Wilcoxon signed-rank test to determine the influence of intravesical or intraurethral stimulation on sensation.

Secondary Aim 1: Assess bladder or urethral current perception threshold (CPT) in women with underactive bladders

Hypothesis: Women with underactive bladder will have increased bladder CPT and increased urethral CPT (reduced sensory nerve activity) compared to normative data in asymptomatic women, and this hypothesis will be evaluated with the Dunn's multiple comparisons test.

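### Do four primary hypotheses without a stated alpha or success rule call for a change to this 20-woman pilot's plan?

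*Combined protocol and SAP*

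**What the plan says.** Purpose of the Study words four primary hypotheses. Three rest on the questionnaire: less bother with bladder stimulation, less bother with urethral stimulation, and more sensation with bladder stimulation. They begin with "The first primary endpoints are that sensory nerve fiber stimulation to the bladder will decrease bothersome urinary symptoms during filling and emptying". The fourth is emptying: "The second primary endpoint is that sensory nerve fiber stimulation to the bladder or urethra will increase bladder emptying during pressure-flow studies". That sentence goes on to restrict emptying to women whose bladder function was poor at baseline.

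Statistical Methods carries the same content in the opposite order. Primary Aim 1 is voided percentage by Wilcoxon signed-rank test. Primary Aim 2 is bother and sensation on the LURN SI-29, by exact McNemar or Wilcoxon. Aim 1 does not repeat the baseline restriction. The Aim 2 title and hypothesis name both bother and sensation, but its method sentence mentions sensation only.

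The Uroflowmetry paragraph, on women who cannot void past the catheters, says "we will still be able to fulfill our primary objectives of improved sensation and improved voiding function" and leaves out bother.

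Data Analysis & Statistical Considerations gives "Expected enrollment n = 20 neurologically-intact women with underactive bladder", an effect size dz of 0.67 and power 0.8, and Statistical Considerations continues: "Our expected enrollment will enable detection of a 7.5% change in voided percentage after stimulation with power (1-beta) of 0.8". It states no alpha or sidedness. Multiplicity methods appear only for secondary aims: Dunn's test for Secondary Aim 1 and Bonferroni for Secondary Aim 2.

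Design & Procedures calls the work a pilot ("Men are excluded from this pilot study due to the high incidence of similar symptoms"). Arm sizes are not fixed in advance: "Participants will be assigned to the intervention arm based on CPT".

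**The concern.** Four hypotheses are labelled primary, and nothing says what counts as success. If any one suffices, the false-positive risk rises above that of a single test. If all are needed, power is low. A rule picked after the data are seen could turn the same results into a positive or a negative primary finding. The plan names multiplicity methods for two secondary aims, so their absence for the primaries looks like an oversight. The differing order, the missing mention of bother in one place and the open choice of test make it harder still to tell which result was meant to be confirmatory. Only voided percentage has a sample-size basis.

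**Working it through.** **Inputs.** n = 20, dz = 0.67 and power 0.8 come from Data Analysis & Statistical Considerations. The four hypotheses come from Purpose of the Study, and the tests from Statistical Methods. Alpha is not stated. Arm sizes follow CPT, so splits (bladder/urethral) of 5/15, 10/10 and 15/5 are examined.

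**1. Recovering alpha.** Paired t power uses noncentrality dz × √n = 0.67 × √20 = 3.00.
- Two-sided 0.05: t-test power 0.811 and smallest n = 20. Exact Wilcoxon power is 0.79.
- One-sided 0.05: t-test power 0.893 and smallest n = 16.

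Two-sided 0.05 reproduces the plan's figures and one-sided 0.05 does not. The level used below is therefore 0.025 per test in the favourable direction. The implied SD of change in voided percentage is 7.5 / 0.67 = 11.2 points.

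**2. Risk if any one favourable result counts, with no mean change.** For independent tests with sizes a₁ to a₄, risk = 1 − Π(1 − aᵢ).
- Full-size tests: 1 − 0.975⁴ = 9.6%. Bound whatever the correlation: 4 × 0.025 = 10%.
- Exact Wilcoxon sizes in the favourable direction: 0 at n = 5, 0.0244 at n = 10, 0.0240 at n = 15, 0.0242 at n = 20. Two hypotheses use the bladder arm, one the urethral arm, and emptying uses all 20.
  - 10/10: 1 − 0.9756³ × 0.9758 = 9.4%
  - 5/15: 1 − 1 × 1 × 0.9760 × 0.9758 = 4.8%
  - 15/5: 1 − 0.9760² × 1 × 0.9758 = 7.0%
- Exact McNemar for the three questionnaire hypotheses is conservative in small arms. With 30% to 100% of women discordant, the risk is 2.6% to 5.8% over these splits.
- Correlation between endpoints lowers the risk. For full-size tests at equal arms it is 8.0% at correlation 0.7.

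**3. Risk if all four must succeed.** It cannot exceed the size of one test, 2.5%, so there is no inflation.

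**4. What depends on the rule when there is an effect.** Simulation used 200,000 trials per setting, a 10/10 split, dz = 0.67 assumed on every endpoint, and correlation 0 to 0.7. The chance of success is 89% to 97% if any one counts, 79% for voided percentage alone, and 7% to 14% if all four must succeed. The documents give no effect size for the questionnaire, so this spread is illustrative.

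**5. Price of formal control.** Bonferroni over four tests uses 0.05 / 4 = 0.0125 two-sided. Power at n = 20 falls to 0.60 (t) or 0.57 (Wilcoxon), and 29 or 30 women would be needed.

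**6. The wording side by side.** Purpose of the Study and Statistical Methods contain essentially the same four hypotheses in a different order, and neither section presents the order as a testing hierarchy. The Uroflowmetry sentence is an aside about a fallback procedure and does not list endpoints. Bother is missing from one method sentence but present in the title and hypothesis directly above it. The two named tests fit the questionnaire's item types: the screening items mix a yes/no item (sensation in the bladder area) with graded ones such as "In the past 7 days, how bothered were you by urinary symptoms". McNemar for the yes/no items and Wilcoxon for the graded ones is the natural reading.

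**The case for a change.** The strongest case for a change is that the plan itself calls these endpoints primary, states hypotheses and claims power, so readers may treat any significant one as confirmatory. Writing down a rule costs only words. Both points are true. The gap is real, and the 7% to 97% spread shows that the label of success depends on the rule.

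The 10% bound also has conditions. It needs two-sided 0.05; at one-sided 0.05 the independent-test figure is 18.5%. It needs one test per hypothesis; six independent tests give 14% and eight give 18%. It needs tests that hold their size. With an uncorrected normal approximation the smallest Wilcoxon p at n = 5 is 0.043, and the 5/15 risk rises from 4.8% to 10.6%.

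Two things weigh against acting on this. First, multiplicity is not the main threat in an uncontrolled before-after study that enrols women for poor scores. An assumed mean drift of 0.2 SD, with no stimulation effect, would make the single 20-woman Wilcoxon test favourable about 13% of the time. No success rule protects against that. Second, the Bonferroni contrast is weak. It accompanies a repeated-measures ANOVA on several cystometric volumes and reads as control within that aim, with no bearing on control across hypotheses.

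One difference of substance remains. Purpose of the Study limits emptying to women with poor function at baseline, and Primary Aim 1 does not. Entry requires two of three criteria, so low voiding efficiency is not required of everyone. If the restriction applied, fewer than 20 women would be analysed, and exact Wilcoxon power would fall from 0.79 to, for example, 0.62 at 14 women. This concerns the analysis set and does not bear on the success rule. Primary Aim 1 and the sizing on 20 both point to analysing all treated women.

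**Conclusion.** The gap exists, but it does not require a change to the plan. The any-one risk is about 3% to 9% (bound 10%), and the all-four risk is at most 2.5%. These figures assume two-sided 0.05, one exact test per hypothesis, emptying pooled over all 20 women, and no mean change. In a 20-woman uncontrolled pilot, whether to control error across primary hypotheses is a matter of judgement.

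The missing details are ones an analyst fills sensibly: two-sided 0.05 from the sizing, each hypothesis reported separately, and the test matched to the item type. The reversed order and the shortened wording are clerical. The only change of substance would make voided percentage the sole confirmatory endpoint. That would demote the symptom endpoints that Purpose of the Study lists first and ties to the overall objective. It would also rest the claim on a test that pools two stimulation sites, because exact Wilcoxon power in a single arm of 10 is only 0.46. That is a fair trade-off for the sponsor to make either way.

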Intravesical (bladder) electrical stimulation This procedure is specific to participants in the bladder stimulation arm. A sterile stimulation catheter (Gaeltec custom catheter, 7-French) will be placed in the bladder through the urethra and the electrode contacts will be positioned to be floating within the bladder. The electrode contacts will be surrounded by ~30 ml of saline infused through the catheter. Impedance measurements will be recorded to monitor electrode integrity. A single return electrode will also be placed on the abdominal skin above the pubic bone. Stimuli will be delivered as 0.2 ms charge-balanced biphasic rectangular current pulses applied between the catheter electrode and the return surface electrode. Stimulation frequency will be set at 20 Hz and amplitude will be adjusted individually to 80% of the maximum tolerable intensity (Jiang and Lindstrom 1999, Gladh et al. 2003). Participants will be instructed to inform the study staff of any unpleasant sensations they may experience and may elect to terminate stimulation at any point. Electrical stimulation will be applied to bladder sensory nerves for up to 60 minutes prior to the start of urodynamic studies (Gladh et al. 2003, Deng et al. 2017).

Intraurethral electrical stimulation This procedure is specific to participants in the urethral stimulation arm. A sterile stimulation catheter (Gaeltec custom catheter, 7-French) will be placed in the urethra and positioned with the electrode contact 10-14 mm from the bladder neck to stimulate the proximal urethral sensory nerves. The catheter and electrode leads will be secured to the participant's leg with medical tape. Impedance measurements will be recorded to monitor electrode integrity. A single return electrode will also be placed on the abdominal skin above the pubic bone. Stimuli will be delivered as 0.2 ms charge-balanced biphasic rectangular current pulses applied between the catheter electrode and the neutral surface electrode. Stimulation frequency will be 10 Hz (may switch 2 or 20 Hz in subsequent participants if unresponsive) and amplitude will be adjusted individually to 80% of the maximum tolerable intensity (Gustafson et al. 2004, Yoo et al. 2011). Electrical stimulation will be applied to urethral sensory nerves at "strong desire to void" during cystometry. The participant will then be given permission to void at

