The potential benefits of the proposed study to research participants are as follows:

- Participants will experience standard procedural risks involved with invasive urodynamics and electrical stimulation. The potential acute benefit of decreased lower urinary tract symptoms (LUTS) and increased bladder emptying is reasonable relative to the risks of additional urodynamic testing that they may have otherwise undergone.

The potential risks for the study are as follows:

- The risk for breach of confidentiality of personally identifiable information. There is minimal risk given our Data and Safety Monitoring Plan but this risk will result in loss of confidentiality of study participation.
- Risk for breach of confidentiality with electronic informed consent. Participants will receive a signed copy of their consent via the email address they provide and this risk is disclosed in the informed consent form.
- Participants will be asked to withdraw medications (e.g., alpha-adrenergic antagonists, cholinergic agonists, cholinesterase inhibitors) that affect urination for 48 hours prior to study participation. This will create a risk of them being untreated for the medicated condition. We do not expect significant complications other than decreased quality of life from 48 hours of medication withdrawal. We will protect against the risk of significant adverse events during medication withdrawal by instructing participants to contact study personnel in the event of adverse effects.
- During invasive urodynamic testing, there is a risk of irritation and infection with catheterization. Participants may develop a urinary tract infection, hematuria, or pain and discomfort. We will minimize the risk of urethral irritation by lubricating the catheter with K-Y jelly and having the fewest de novo catheterizations possible Additionally, we will minimize the risk of infection by using sterile preparation techniques, as well as antiseptic cleaning of the working area.

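### The urethral arm's primary symptom endpoint measures carry-over across an essentially unstimulated week, not symptoms during stimulated emptying, and should be defined and interpreted that way

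*Combined protocol and SAP*

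**What the plan says.** **The claim.** Objectives & hypotheses lists among the first primary endpoints that "stimulation to the urethra will decrease bothersome urinary symptoms during emptying", judged by the symptom questionnaire. Primary Aim 2 under Statistical Methods repeats it: "intraurethral stimulation will decrease affirmatory responses to bothersome symptoms during emptying".

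**The exposure.** The Intraurethral electrical stimulation section says "Electrical stimulation will be applied to urethral sensory nerves at" the point of strong desire to void during cystometry. The woman then voids at maximum cystometric capacity with the current still on. No second session and no home stimulation are described. The possible change of frequency applies to later participants, not to a repeat in the same woman.

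**The measurement.** Under Study procedure visit, the LURN SI-29 is completed on the visit day before stimulation. The second and last is "a post-study condition LURN SI-29 questionnaire that will be emailed via RedCap 7 days after the study visit", after which "At that time, they will be considered to have completed the study". The full instrument is not reproduced, but all five items shown under Inclusion Criteria use a seven-day recall, for example "In the past 7 days, how often did you feel that your bladder was not completely empty after urination".

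**The expected benefit.** The Risk/Benefit Assessment speaks of "The potential acute benefit of decreased lower urinary tract symptoms (LUTS) and increased bladder emptying".

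**The concern.** The hypothesis is worded as an effect of stimulation on symptoms during emptying. The questionnaire that tests it asks about a week in which, apart from the study void, every void is made without stimulation. No section says that one stimulated void is expected to ease symptoms for a week, and the one description of the benefit's time course calls it acute.

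What is at stake is the reading of the result. An unchanged day-7 LURN could be reported as showing that urethral stimulation does not help emptying symptoms, although symptoms under stimulation were never asked about. An improved day-7 LURN could be reported as confirming the hypothesis, although the design has nothing to set it against.

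**Working it through.** **1. The plan's own figure.** Data Analysis & Statistical Considerations gives n = 20, dz = 0.67 and power 0.8. For a paired t-test, power is the probability that a noncentral t (n − 1 df, noncentrality dz × √n) exceeds the critical value. Two-sided alpha 0.05 is assumed, since none is stated. With n = 20, noncentrality is 0.67 × √20 = 3.00 and power is 0.81, so the figure reproduces. It is tied to a 7.5% change in voided percentage and uses all 20 women. No effect size or power is given for the LURN. If 10 women entered the urethral arm (an assumption; arm sizes follow from CPT), the same dz would give power of about 0.47 (noncentrality 0.67 × √10 = 2.12). A null would then be weak on size alone, whatever the timing.

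**2. Exposure set against recall.**

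| | Baseline LURN | Day-7 LURN |
|---|---|---|
| Completed | visit day, before stimulation | from an email 7 days after the visit |
| Period recalled | week before the visit | week after the visit |
| Voids under urethral stimulation | none | at most the visit void |

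*At most one* is inferred from the single fill-and-void sequence described; no section states a number. CPT testing also stimulates the urethra, but not during voiding. No completion window is given, so a reply even a day late moves the visit out of the recalled week.

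**3. Share of the recalled week that was stimulated.** Voids per day are not in the documents; assume 5 to 10.

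- 7 × 5 = 35 voids, and 1/35 = 2.9%
- 7 × 10 = 70 voids, and 1/70 = 1.4%
- 0% if the visit falls outside the recall

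This is a share of exposure. It is not a ceiling on the effect, because carry-over could change the other voids.

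**4. What each result can show.**

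- *Null:* no carry-over was detected. Nothing follows about symptoms while the current is on.
- *Positive:* compatible with carry-over, but also with expectation and regression to the mean. Allocation is by CPT, and no sham or unstimulated group is described. Entry needs two of three criteria, and only one of these (voiding efficiency) is not a symptom report, so every woman is selected on at least one recent symptom answer. The baseline LURN is taken after the phone screen, so some regression will already have occurred; the remainder cannot be ruled out. For women on relevant drugs, the 48-hour withdrawal also falls inside the baseline week, and the time of restart is not stated.

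**5. Sequence at the visit.** Study procedure visit places urodynamics after the stimulation session, and the Pressure-flow study paragraph also speaks of voiding after stimulation. The Intraurethral electrical stimulation and Cystometry sections place urethral stimulation during urodynamics. Either reading leaves the following week unstimulated.

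**The case against.** The strongest reply is that the timing may be deliberate. A seven-day recall sent on day 7 gives a post-visit window that matches the baseline window, and the hypothesis is written as a change in LURN responses. The Background describes natural reflex physiology and does not say that the effect of electrical stimulation ends with the current; the word acute is not defined. All of this stands. Carry-over is a legitimate thing to measure, but the plan does not say that this is what it measures.

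Three stronger readings are tempting, and the documents do not support them.

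- *The trial cannot show whether urethral stimulation eases emptying.* Voided percentage is itself primary and, by the intraurethral procedure, is recorded with the current on. Only a symptom rating of that void is missing.
- *One void in 35 to 70 limits how far the LURN could move.* That assumes no carry-over, which is the open question. It also fits frequency items better than the global satisfaction and bother items shown.
- *A positive result would most likely be expectation or natural change.* The text supports only that these cannot be separated from a treatment effect. That ambiguity comes from the lack of a control, not from the timing.

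It is also fair to object that comparing the stimulated void with the void made before CPT would not isolate stimulation. The earlier void is catheter-free and at whatever volume is present; the later one follows retrograde filling and is made around catheters with perceptible current. That limits what the fix can claim.

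**Conclusion.** The mismatch holds for the urethral arm's LURN endpoint. As described, it measures change over an essentially unstimulated week after one session, while Objectives & hypotheses and Primary Aim 2 present it as a test of stimulation on emptying symptoms. A null would not bear on the effect under stimulation, and a positive result could not be attributed to stimulation.

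No stated figure changes. Under the assumed void frequency, the stimulated void is 1.4% to 2.9% of those recalled, or none. The conclusion rests on two inferences: that the single sequence described is the whole exposure, and that the full LURN shares the recall period of the items shown.

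The point does not reach voided percentage. The bladder arm shares the day-7 timing and the lack of a control, but it receives up to 60 minutes of stimulation before urodynamics and is not the subject here.

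**What to change.** 1. In Objectives & hypotheses and Primary Aim 2, define the urethral-arm LURN endpoint as the change in symptoms over the week after a single session (carry-over), and limit conclusions to that. Record the date on which the questionnaire is completed.
2. Straight after the stimulated void, ask two or three void-specific questions on emptying symptoms and bother, for example hesitancy, straining, slow stream or incomplete emptying. Ask the same after the void made before CPT, as context. Report both as supportive and descriptive.
3. Reconcile the sections that place urodynamics after urethral stimulation with those that place stimulation during urodynamics.

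The cost is a few questions asked twice at an existing visit, plus wording; no extra visit, procedure or participant is needed. The downsides should be stated: single-void items are not validated, the rating is unblinded, and the two voids differ in catheters, filling and volume. The within-visit difference therefore supplements the LURN and does not isolate the effect of stimulation.
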